According to the recently published results of TURQUOISE III study Gt1b patients with cirrhosis can be successfully treated with 3D regimen without ribavirin [6]. In this study treatment-naïve and peginterferon/ribavirin treatment-experienced patients received 12 weeks of therapy with ombitasvir/paritaprevir/ritonavir (25/150/100 mg once daily) and dasabuvir (250 mg twice daily). Key inclusion criteria were hemoglobin ≥ 10 g/dL, albumin ≥ 2.8 g/dL, platelet count $\geq 25 \times 10^9/L$, creatinine clearance ≥ 30 ml/min, and Child-Pugh score ≤ 6 . Efficacy was assessed by the percentage of patients achieved sustained virologic response (HCV RNA < 25 IU/mL) 12 weeks post-treatment (SVR12). Efficacy and safety were assessed in all patients receiving study drug. Sixty patients with HCV GT1b infection and cirrhosis received treatment. The study population comprised 62% male, 55% treatment-experienced, 83% with IL28B non-CC genotype, 22% with platelet count $< 90 \times 10^9/L$, and 17% with albumin < 3.5 g/dL. All 60 patients completed treatment, and SVR12 was achieved in 100% (95% CI, 94.0 – 100%) of patients. The most common adverse events were fatigue (22%), diarrhea (20%), and headache (18%). Only one patient (1.7%) experienced a serious adverse event. Laboratory abnormalities were infrequently observed and not clinically significant. The HCV regimen of ombitasvir/paritaprevir/ritonavir and dasabuvir without ribavirin for 12 weeks achieved 100% SVR12 and was well tolerated in HCV GT1b-infected patients with cirrhosis, suggesting that this 12-week ribavirin-free regimen is sufficient in this population.

Current study was developed in order to assess RWE effectiveness and safety of 3D regimen without RBV in Gt1b patients with compensated cirrhosis in Russia.

8.0**Research Question and Objectives****8.1****Research Question**

- What is the effectiveness of the interferon-free 3DAA ABBVIE REGIMEN without RBV in patients with HCV Gt1b infection and compensated liver cirrhosis in a real life setting?

8.2**Objectives****8.2.1****Primary Objective**

- To describe the effectiveness of the interferon-free 3DAA ABBVIE REGIMEN without RBV in patients with HCV Gt1b infection and compensated liver cirrhosis as evidenced by sustained virological response at 12 weeks after the end of treatment in routine clinical practice.

8.2.2**Secondary Objectives**

- To describe the end-of-treatment (EoT) response rate

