9.13.6 Statistical Methods for Analysis of Effectiveness Variables

The simple percentage of patients achieving SVR12 will be calculated and an exact two-sided 95% confidence interval (CI) of the percentage will be computed based on the Clopper-Pearson method.

Corresponding methods will be used for other response rates (EoT response rate, relapse rate). The relapse rates will be estimated in patients of the CP analysis groups with EoT response and sufficient HCV RNA measurements post-treatment.

These analyses will be of exploratory nature, data driven, and will be repeatedly performed for various CP Analysis Groups, since not each covariate might be predictive in each patient group. Furthermore, the fact that treatment regimens will differ in the various patient groups has to be taken into account, when selecting the patient groups for each MLR analysis. Backward selection procedures will be applied to generate the final MLR models which consider only covariates in the selection procedure with a p-value <0.25 in the corresponding univariate logistic regression analysis. A p-value <0.05 will be used for the covariates to stay in the model in a backward elimination step. Logistic regression methods will also be used to investigate the impact of treatment adherence on SVR12.

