4.1 Sample size¹

60 patients will be included in this descriptive study without any prior sample size calculation.

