4.3 Planned analyses

The only final statistical analysis report will be performed for this study.

No analyses for DMC meetings and no interim analysis are planned in the study.

5 General considerations

Study Day will be calculated from the reference start date, and will be used to show start/stop day of assessments and events.

Reference start date is defined as the day of the start treatment (“EXSTDTC” variable from “EX” domain of the database).

If the date of the event is on or after the reference date then

study day = (date of event – reference date) + 1.

If the date of the event is prior to the reference date then

study day = (date of event – reference date) – 1.

Baseline is defined as the measurement taken on Visit 1.

6 Analysis populations

The target population (TP) – all patients with signed written Patient Authorization, who fulfill the eligibility criteria. Patients who prematurely discontinue earlier than ≤study day 55 will be used in analyses on the target population with actual EoT time point without windowing conventions adjustment for EoT.

The core population (CP) – all patients of the TP, who have started and received the treatment combination recommended in the current local label for their disease characteristics. Patients with EoT ≤ study day 55 (less than 8 weeks) will be excluded from the CP (these patients will be included to the NCP).

The safety population (SP) – all patients who received at least one dose of the ABBVIE REGIMEN.

The non-core population (NCP) – patients not receiving the treatment recommended in the local label.

The core population with sufficient follow-up data (CPSFU) – all CP patients, who fulfill one of the following criteria:

- evaluable HCV RNA data within the SVR12 time window;

¹ This section is based on the section 9.1.1 “Study Size” of clinical study Protocol.

P16-253 (CITRIN) _ STATISTICAL ANALYSIS PLAN _ FINAL 2.0 _ 16 Mar 2018

- a HCV RNA value ≥ 50 IU/mL at the last measurement post-baseline (i.e. no virological response achieved at the last measurement on-treatment or post-treatment);
- HCV RNA <50 IU/mL at the last measurement post-baseline, but no HCV RNA measurement on the SVR12 visit due to reasons related to safety (e.g. dropped out due to AE) or incomplete efficacy information (e.g. virologic failure such as relapse is reported in the eCRF but date and value of the corresponding HCV RNA test is missing).

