 - relapse after EoT (HCV RNA value <50 IU/mL or undetectable/negative at EoT or at the last on-treatment HCV RNA measurement followed by HCV RNA \geq 50 IU/mL or positive post-treatment);
 - failure to suppress (each measured on-treatment HCV RNA value \geq 50 IU/mL or positive);
 - premature study drug discontinuation with no on-treatment virologic failure;
 - missing SVR12 data and/or none of the above criteria.

Figure 9.1 illustrates the patient's distribution by SVR12 response/non-response categories.

P16-253 (CITRIN) _ STATISTICAL ANALYSIS PLAN _ FINAL 2.0 _ 16 Mar 2018

[figure not shown]

Figure 9.1 – Patient's distribution by SVR12 response/non-response categories. Frequencies and percentages with 95% confidence intervals will be calculated for each effectiveness outcomes and will be presented according the section 7.1. Also frequency tables will be repeated for patients in subgroup without missing SVR12 data category.

Effectiveness endpoints (SVR12 achieving, virological response at EoT and relapse after EoT) will be analyzed using univariate logistic regression, if applicable. These analyses will be of exploratory nature, data driven, and will be repeatedly performed for various CP analysis groups, since not each covariate might be predictive in each patient group.

The following parameters can be included in the univariate models as explanatory variables (fixed effect or covariate):

- treatment experience (with/without prior treatment for CHC);
- Child Pugh score;
- result of FibroTest;
- history of liver decompensation;
- age;
- gender;
- race;
- BMI;
- laboratory hematology¹:
 - hemoglobin;
 - platelets;
 - prothrombin time;
 - laboratory clinical chemistry:
 - ALT;

¹ Note that all Hematology variables and all Clinical Chemistry should be in the same units. If it is impossible to bring units to the same the smallest units groups will be accepted as missing. If it is impossible to identify the smallest units groups the corresponding covariate will be deleted from the analysis.

P16-253 (CITRIN) _ STATISTICAL ANALYSIS PLAN _ FINAL 2.0 _ 16 Mar 2018

- AST;
- Gamma-GT;
- total bilirubin;
- albumin;
- creatinine clearance;
- alpha-1-fetoprotein.

Additionally, after univariate model analyses all effectiveness endpoints can be analyzed using MLR (if applicable) which consider only covariates in the selection procedure with a p-value <0.25 in the corresponding univariate logistic regression analysis¹.

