Program code, date, time

Data extracted: DD.MM.YYYY

Similar to table for SVR12 achieving univariate logistic regression results, tables for the following variables (outcomes) will be constructed (if applicable):

Table 2.1.X.1 Virological response at EoT. Univariate logistic regressions results
Table 2.1.X.2 Virological response at EoT. Multiple logistic regression results

Table 2.1.X.1 Relapse after EoT. Univariate logistic regressions results
Table 2.1.X.2 Relapse after EoT. Multiple logistic regression results

P16-253 (CITRIN) _ STATISTICAL ANALYSIS PLAN _ FINAL 2.0 _ 16 Mar 2018**Effectiveness Analyses (CP)**

Similar to tables 2.1.1.X-2.1.2.X, the following tables will be constructed for the core population:

Table 2.2.1.1 Percentage for effectiveness endpoints

Table 2.2.2.1 Percentage for effectiveness endpoints without patients with missing SVR12 results

Similar to tables 2.1.X.1-2.1.X.2, tables for the following variables (outcomes) will be constructed (if applicable) for the core population:

Table 2.2.X.1 SVR12 achieving. Univariate logistic regression results

Table 2.2.X.2 SVR12 achieving. Multiple logistic regression results

Table 2.2.X.1 Virological response at EoT. Univariate logistic regressions results

Table 2.2.X.2 Virological response at EoT. Multiple logistic regression results

Table 2.2.X.1 Relapse after EoT. Univariate logistic regressions results

Table 2.2.X.2 Relapse after EoT. Multiple logistic regression results

P16-253 (CITRIN) _ STATISTICAL ANALYSIS PLAN _ FINAL 2.0 _ 16 Mar 2018

Effectiveness Analyses (CPSFU)

Similar to tables 2.1.1.X-2.1.2.X, the following tables will be constructed for the core population with sufficient follow-up data (CPSFU):

Table 2.3.1.1 Percentage for effectiveness endpoints (main analysis)

Table 2.3.2.1 Percentage for effectiveness endpoints without patients with missing SVR12 results (main analysis)

Similar to tables 2.1.X.1-2.1.X.2, tables for the following variables (outcomes) will be constructed (if applicable) for the core population:

Table 2.3.X.1 SVR12 achieving. Univariate logistic regression results

Table 2.3.X.2 SVR12 achieving. Multiple logistic regression results

Table 2.3.X.1 Virological response at EoT. Univariate logistic regressions results

Table 2.3.X.2 Virological response at EoT. Multiple logistic regression results

Table 2.3.X.1 Relapse after EoT. Univariate logistic regressions results

Table 2.3.X.2 Relapse after EoT. Multiple logistic regression results

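### The repeated effectiveness tables that leave out missing SVR12 have no rule to keep informative failures, and in CPSFU the repeat undoes criterion 3

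*SAP*

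**What the plan says.** SAP section 9 analyses effectiveness in TP, CP and CPSFU. Patients who do not achieve SVR12 are sorted into breakthrough, relapse after end of treatment (EoT), failure to suppress, "premature study drug discontinuation with no on-treatment virologic failure", and a last category, "missing SVR12 data and/or none of the above criteria". The full shells (Table 2.1.1.1 and its CP and CPSFU counterparts) list missing SVR12 under non-response, with the whole population as denominator. This agrees with protocol 9.13.1, where an HCV RNA value still missing after imputation counts as virological failure. Protocol 9.13.3 places the primary analysis on all CP patients.

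Section 9 then adds: "Also frequency tables will be repeated for patients in subgroup without missing SVR12 data category". The protocol does not plan this repeat. The CPSFU shell is headed "Table 2.3.2.1 Percentage for effectiveness endpoints without patients with missing SVR12 results" and carries a main-analysis label, as does the full CPSFU table, 2.3.1.1.

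Under SAP section 6, CPSFU criterion 3 keeps a patient whose last value was a response but who has "no HCV RNA measurement on the SVR12 visit due to reasons related to safety (e.g. dropped out due to AE) or incomplete efficacy information". The example given for incomplete information is a relapse recorded in the eCRF without date or value. Section 6 states that the only patients left out are those whose last measurement showed response and whose SVR12 is missing for reasons unrelated to safety or effectiveness.

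**The concern.** An SVR12 success cannot fall in the missing category, so leaving it out removes only non-successes. That is harmless if all of them are responders who were lost for unrelated reasons. It is not harmless if some are failures, and the plan foresees this: Table 1.2 lists death and insufficient virological response among the reasons for having no SVR12 test.

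Two features make it worse.

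- **The excluded set is not fixed.** The first list in section 9 and the shell row refer to missing SVR12 data. The definition in section 9 adds patients who meet no other criterion. The shell titles refer to missing SVR12 results. These are different sets of patients.
- **The CPSFU repeat works against CPSFU.** A criterion 3 patient has no SVR12 measurement by definition. Under the shell title, the repeat removes exactly the patients whom criterion 3 was written to keep.

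Because the repeated CPSFU table is labelled as a main analysis, its rate could be reported as a headline result. It would be read against the cited 60-patient study, where SVR12 was 100%, so a shift of a few points matters to the reader.

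**Working it through.** **Inputs**

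- Planned size (SAP, Sample size): "60 patients will be included in this descriptive study without any prior sample size calculation".
- Interval (protocol 9.13.6): "an exact two-sided 95% confidence interval (CI) of the percentage will be computed based on the Clopper-Pearson method".
- The only rate in the documents that can be recomputed (protocol 7.0): "All 60 patients completed treatment, and SVR12 was achieved in 100% (95% CI, 94.0 – 100%) of patients".
- The number of patients in the missing category, and the number of true failures among them, are not given. Assumed range: 1 to 9 of 60, with anywhere from none to all being failures.

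**Reproducing the stated figure.** For 60/60 the Clopper-Pearson lower limit is 0.025^(1/60) = 0.940, so the interval is 94.0–100%, as stated.

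**Who can be dropped under each wording**

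| Patient | Section 9 definition | Shell title |
|---|---|---|
| Responder lost for unrelated reasons | dropped | dropped |
| Treatment completer, SVR12 missing because of death or AE | dropped | dropped |
| Relapse in eCRF without date or value | can be dropped | dropped |
| SVR12 sample positive, no on-treatment HCV RNA | dropped (fits no other category) | kept (has a result) |
| Documented breakthrough or relapse, no later SVR12 sample | depends on Figure 9.1 | depends on Figure 9.1 |

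**Formulas.** Let v be the failures that stay in the repeat, m the excluded patients, and f the true failures among those m. The number with SVR12 is 60 − v − m in every table.

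- Full table: (60 − v − m)/60
- Repeated table: (60 − v − m)/(60 − m)
- Rule that keeps true failures: (60 − v − m)/(60 − m + f)

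**Illustration (assumed counts, CP = 60).** 55 SVR12, 1 classified relapse, 2 responders lost for unrelated reasons, 1 completer with SVR12 missing because of death or AE, 1 SVR12-positive with no on-treatment HCV RNA.

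| Table | Dropped | SVR12 (95% CI) |
|---|---|---|
| Full CP | 0 | 55/60 = 91.7% (81.6–97.2) |
| Only the two unrelated losses removed (same as full CPSFU) | 2 | 55/58 = 94.8% (85.6–98.9) |
| Repeat, shell-title rule | 3 | 55/57 = 96.5% (87.9–99.6) |
| Repeat, whole section 9 category | 4 | 55/56 = 98.2% (90.4–100.0) |

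The shell-title rule adds 96.5 − 94.8 = 1.7 points for one failure dropped. The section 9 wording adds 98.2 − 94.8 = 3.4 points for two.

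**Range**

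- One true failure dropped: from 57/59 − 57/60 = 96.6 − 95.0 = 1.6 points (v = 2, m = 1) to 51/51 − 51/52 = 100 − 98.1 = 1.9 points (v = 0, m = 9).
- No true failure dropped (f = 0): the repeated table and the rule that keeps failures coincide, so the excess is 0. With v = 2 and m = 9, the repeat gives 49/51 = 96.1% against a full-data rate of 58/60 = 96.7%, a gap of 0.6 points. The full table is then too low, by between 1/60 = 1.7 and 9/60 = 15.0 points.
- All nine dropped patients are failures (v = 0, m = 9): 51/51 = 100% against 51/60 = 85.0%, an excess of 15.0 points.

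**The case against.** The strongest reply is that the repeat is an addition. The primary CP estimate and all three full tables count missing as failure, and protocol 9.15 itself warns that missing HCV RNA can make the SVR rate too low. Setting a missing-equals-failure table, a CPSFU table and an observed-case table side by side is a defensible way to show the range. This stands. It is why the point is confined to the repeated tables.

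A reader might infer that the study's SVR12 result as a whole is biased upward, or that the repeat always overstates effectiveness. The documents support neither. The full tables are untouched, and if every dropped patient is in fact a responder the repeat has no upward shift.

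A reader might also infer that the whole residual category is certainly removed, including SVR12-positive patients. That follows only from the section 9 definition. Under the shell title such a patient has a result and stays in as non-response.

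Patients who stop treatment early have their own category, and the repeated shell keeps that row along with those for breakthrough, relapse and failure to suppress. How a patient is placed who meets one of these and also lacks an SVR12 sample depends on Figure 9.1, which is not available here. No claim is made that they are lost.

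What the reply does not supply is a rule. Nothing in the SAP keeps safety-related missing results, or relapses reported without a value, in the repeated tables. Nor does it explain why a table that removes criterion 3 patients is labelled as a main analysis.

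**Conclusion.** The concern holds for the repeated tables only. They lack a rule to keep known or informative failures, the excluded set is described in ways that do not agree, and the CPSFU repeat defeats the purpose of criterion 3 while labelled as a main analysis, against a protocol whose primary analysis is on all CP patients.

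The rate in a repeated table is inflated when, and only when, a true failure is dropped, by about 1.6 to 1.9 points each with 60 patients. In the illustration this is 1.7 points under the shell title. The 98.2% figure applies only if the whole residual category is dropped. All counts other than the planned 60 are assumptions. That the category will contain failures is possible, not shown.

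The SAP should be changed, but this is not a threat to the primary estimate.

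**What to change.** 1. Define the excluded subgroup once, by the rule section 6 already uses: last post-baseline HCV RNA value a response, and SVR12 missing for reasons unrelated to safety or effectiveness.
2. Keep as non-response in every table: a positive SVR12 sample, a relapse reported without date or value, and SVR12 missing for safety reasons.
3. Use the same wording in both section 9 lists, in the table list in 16.1 and in the shell titles. The table numbers need aligning too: the CPSFU repeat is 2.3.1.2 in 16.1 and 2.3.2.1 in the shells.
4. Delete the CPSFU repeat, which under this rule excludes nobody. The CP repeat would then essentially reproduce full CPSFU Table 2.3.1.1.
5. Reconcile the main-analysis labels on both CPSFU tables with the primary analysis on all CP patients.
6. If a pure observed-case table is still wanted for TP or CP, label it as a sensitivity analysis and show the number of excluded patients and their reasons beside it.

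The cost is a little rewording and one derived flag. The reasons for having no SVR12 test are already to be tabulated (SAP 8.1 and Table 1.2). The supplementary SVR12 figure may come out slightly less favourable.

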In total, there will be at least four study visits. Patients who prematurely discontinue the study should return to the site to document EoT data.

The schedule of the study procedures is presented in table 4.1.

Table 4.1 – Program activities

| Assessment/ Procedure (only available data to be collected; no diagnostic or monitoring procedures to be applied to the patients apart from those of routine clinical practice) | Visit 1 | Treatment period | | Post-treatment period | |
|--|---------|------------------------------|------------------------|-----------------------|-----------------|
| | | EoT (on-treatment visits) | Safety Follow-up visit | SVR12 | Follow-up visit |
| Written patient authorization form | X | | | | |
| Inclusion/Exclusion Criteria | X | | | | |
| Demographic information | X | | | | |
| IL28B | X | | | | |
| Relevant CHC disease characteristics | X | | | | |
| Liver fibrosis stage | X | | | | |
| CHC treatment history | X | | | | |
| HCV genotype and subtype | X | | | | |
| HCV RNA samples | X | X | | | X |
| Clinical chemistry and hematology | X | X | | | X |
| ABBVIE REGIMEN initiation documentation | X | | | | |
| ABBVIE REGIMEN adherence | X | | X | | |
| Concomitant medication | X | X | | | X |
| Relevant medical history, co-morbidities | X | | | | |
| SAE, non-serious AE and pregnancy reporting | X | X | X | X | X |

Time windows for reported clinical laboratory test results are described in the table 4.2.

Table 4.2 – Analysis time windows

| Time point | Time Window |
|------------------|--|
| Visit 1 | Last value prior to start of study treatment (i.e. \leq study day 1) |
| EoT ¹ | Study day of last dose (from study day 56 to study day 98) |
| SVR12 | last value between 57 and 112 days post the study day of last dose |

¹ The EoT time window will not be used for the target population analyses, actual collected EoT visit will be presented in this case even if $EoT \leq$ study day 55 (less than 8 weeks).

P16-253 (CITRIN) _ STATISTICAL ANALYSIS PLAN _ FINAL 2.0 _ 16 Mar 2018

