To avoid the multicollinearity problem all possible explanatory variables will be examined using following SAS script:

```
ods graphics on;
PROC CORR data=<dataset> plots=all;
VAR <variables>;
RUN;
ods graphics off;
```

Statistical significant correlated variables with correlation coefficient ≥ 40 should be considered and managed. All solutions about an explanatory variables choosing will be of exploratory nature, data driven, and will be described with presenting of results of the "PROC CORR" SAS procedure.

Backward selection procedures will be applied to generate the final MLR models esing the SAS procedure LOGISTIC with statement SELECTION = BACKWARD and SLENTRY = 0.05. A p-value <0.05 condition will be used for the covariates to stay in the model in a backward elimination step.

Odds ratio with 95% Wild CI, p-values will be presented for each predictor.

All data for effectiveness analyses will be listed in separate listings (for each effectiveness analyses endpoint).

10 Safety analysis

Safety analysis will be conducted on *the safety population (SP)*.

The following parameters will be analyzed:

- study drug exposure;
- adverse events;
- pregnancies;
- clinical laboratory evaluations.

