10.1 Exposure

Tables with descriptive statistics in accordance with section 7.1 will be presented for the following parameters:

- actual duration ABBVIE REGIMEN (in days);

¹ Note that MLR is possible ONLY if more than one explanatory variables will have a p-value <0.25 in the corresponding univariate logistic regression analysis.

P16-253 (CITRIN) _ STATISTICAL ANALYSIS PLAN _ FINAL 2.0 _ 16 Mar 2018

- the number of patients with collected deviating duration reasons;
- adherence ABBVIE REGIMEN (calculated for Paritaprevir/R-Ombitasvir and for Dasabuvir separately):
 - percentage of target dose taken in treatment intervals (weeks 1-4, 5-8 and 9-12) for Paritaprevir/R-Ombitasvir and for Dasabuvir;
 - percentage of patients who missed of study drug administration for at least 7 days in a row.

All corresponding listings will be presented.

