| Patients with breakthrough (at least one documented HCV RNA value <50 IU/mL followed by HCV RNA \geq 50 IU/mL during treatment) | XX (XX.X) [XX.XX - XX.XX] |
| Failure to suppress (each measured on-treatment HCV RNA value \geq 50 IU/mL) | XX (XX.X) [XX.XX - XX.XX] |
| Patients with relapse (HCV RNA value <50 IU/mL at EoT or at the last on-treatment HCV RNA measurement followed by HCV RNA \geq 50 IU/mL post-treatment) | XX (XX.X) [XX.XX - XX.XX] |
| Patients with premature study drug discontinuation with no on-treatment virological failure (breakthrough or failure to suppress) | XX (XX.X) [XX.XX - XX.XX] |
| Patients with virological response (HCV RNA <50 IU/mL) at EoT | XX (XX.X) [XX.XX - XX.XX] |

N: the number of subjects in the target population. n: number of subjects within a specific category. Percentages are calculated as $100 \times (n/N)$.
 EoT: end of treatment. SVR12: sustained virological response at 12 weeks after end of treatment. CI[^] confidence interval.
 95% confidence intervals calculated using the Clopper-Pearson method.

Program code, date, time

Data extracted: DD.MM.YYYY

P16-253 (CITRIN) _ STATISTICAL ANALYSIS PLAN _ FINAL 2.0 _ 16 Mar 2018

 AbbVie LLC
 P15-743 (HCV RWE)

Table 2.1.X.1 SVR12 achieving. Univariate logistic regression results

 The core population
 Page X of X

| | Total |
|------------------------------|-----------------------|
| Predictor 1 | |
| Patients for analysis (n) | XXX |
| Convergence criterion status | XXXXXXXXXXXXXX |
| OR (95% Wald CI) | X.XXX (X.XXX - X.XXX) |
| p-value | 0.XXXX |
| Predictor 2 | |
| Patients for analysis (n) | XXX |
| Convergence criterion status | XXXXXXXXXXXXXX |
| Reference level | XXXXXXXXXXXXXX |
| OR (95% Wald CI) for Level X | X.XXX (X.XXX - X.XXX) |
| p-value for Male | 0.XXXX |
| ... | |

SVR12: sustained virological response at 12 weeks after end of treatment. OR: odds ratio. CI: confidence interval.

Program code, date, time

Data extracted: DD.MM.YYYY

P16-253 (CITRIN) _ STATISTICAL ANALYSIS PLAN _ FINAL 2.0 _ 16 Mar 2018

 AbbVie LLC
 P15-743 (HCV RWE)

Table 2.1.X.2 SVR12 achieving. Multiple logistic regression results

 The core population
 Page X of X

| | Overall |
|---------------------------|-----------------------|
| Patients for analysis (n) | XXX |
| Predictor 1 | |
| OR (95% Wald CI) | X.XXX (X.XXX - X.XXX) |
| p-value | 0.XXXX |
| ... | |

SVR12: sustained virological response at 12 weeks after end of treatment. OR: odds ratio. CI: confidence interval.

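### Without a planned refit, patients missing any covariate that passes the p<0.25 screen stay out of the final multiple logistic regression, so its exploratory odds ratios can rest on a smaller, selected subset

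*SAP*

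**What the plan says.** SAP section 9 lists 18 covariates that may be examined univariately: eight clinical or demographic items, including "result of FibroTest", three haematology items and seven chemistry items. Multiple logistic regression (MLR) is optional. Its models are ones "which consider only covariates in the selection procedure with a p-value <0.25 in the corresponding univariate logistic regression analysis", and a footnote to section 9 adds that "MLR is possible ONLY if more than one explanatory variables will have a p-value <0.25". Correlated covariates are dealt with before selection. Then "Backward selection procedures will be applied to generate the final MLR models" in the SAS procedure LOGISTIC with "SELECTION = BACKWARD and SLENTRY = 0.05", and a covariate must have p<0.05 to stay.

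Four other provisions bear on missing covariates:

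- The schedule of activities (SAP Table 4.1, Protocol Table 2) says "only available data to be collected; no diagnostic or monitoring procedures to be applied to the patients apart from those of routine clinical practice".
- Protocol section 9.13.1 rules out imputation except for the HCV RNA endpoints. SAP section 7.3 covers only incomplete adverse event dates.
- A footnote in SAP section 9 sets laboratory values in the smallest unit groups to missing when units cannot be reconciled.
- The MLR table shell has one row for the number of patients analysed. It has no row for the number of failures and no second row for a refit.

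**The concern.** Each univariate model uses whoever has that covariate. The multivariable sequence uses only patients who have all the covariates that passed. Backward elimination starts with every candidate in the model, and PROC LOGISTIC fixes its complete-case set at that point. A patient who lacks one candidate is left out at every step, including the steps after that candidate has been dropped. The final model can therefore exclude patients because of a variable it no longer contains.

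Missing values are to be expected. Data are recorded only if routine practice produces them. FibroTest is one staging method beside elastography, and the shell of Table 1.6.1 gives each its own n. Values lost through units that cannot be reconciled would tend to cluster by laboratory, and so by site.

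At stake are the exploratory odds ratios. Patients, and possibly some of the few failures, would be lost needlessly. Those kept would be the ones with the fullest work-up, and the univariate and multivariable tables could describe different patients.

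**Working it through.** **Inputs from the documents.** N is at most 60: "60 patients will be included in this descriptive study without any prior sample size calculation". There are 18 listed covariates (8 + 3 + 7), the entry rule is univariate p<0.25, and covariates are not imputed. The documents state no model n and no missingness rate, so there is no figure to reproduce.

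**Assumptions.** Values are missing independently across covariates. Each routine covariate is 95% or 98% complete. FibroTest is available in 50% or 80% of patients. The starting model has five candidates. Five is a reasonable illustration: if no covariate had any effect, about 18 × 0.25 = 4.5 would be expected to pass the screen.

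**Expected patients in the starting model, which stay fixed through elimination**

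| Five candidates | Formula | 95% complete | 98% complete |
|---|---|---|---|
| No FibroTest | 60 × p^5 | 60 × 0.774 = 46.4 | 60 × 0.904 = 54.2 |
| FibroTest, 50% available | 60 × 0.5 × p^4 | 30 × 0.815 = 24.4 | 30 × 0.922 = 27.7 |
| FibroTest, 80% available | 60 × 0.8 × p^4 | 48 × 0.815 = 39.1 | 48 × 0.922 = 44.3 |

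If all five candidates were fully recorded, nobody would be lost.

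**Expected patients after a refit on the retained covariates.** With one routine covariate retained, 60 × 0.95 = 57.0 or 60 × 0.98 = 58.8. With two retained, 60 × 0.95² = 54.2 or 60 × 0.98² = 57.6. If FibroTest itself is retained, a refit cannot recover patients who lack it.

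**How often FibroTest would enter.** It must first pass p<0.25 among the patients who have it. Assume 3 failures among 60 (an SVR12 of 95%, which is an assumption) and FibroTest missing at random. The chance that no failure has a FibroTest result, so that its univariate model cannot be estimated, is (1 − availability)³:

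- 20% available: 0.8³ = 51%
- 50% available: 0.5³ = 12.5%
- 80% available: 0.2³ = 0.8%

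A simulation under the same assumptions (continuous covariate, Wald p<0.25, 4,000 runs per case) gave these approximate rates of passing the screen:

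| FibroTest available | No effect | 1-SD difference |
|---|---|---|
| 20% | 3% | 5% |
| 50% | 15% | 32% |
| 80% | 22-24% | 58-59% |

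The sparser the test, the greater the loss if it enters, but the less often it enters.

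**The case against.** The strongest reply is that this is conditional and of low consequence. MLR is optional and labelled exploratory. It needs at least two covariates to pass the screen, and the choice of explanatory variables is declared data driven and is to be described, which leaves room to drop a sparse covariate. The shells already show the number of patients for each univariate predictor and for the MLR, so a shrinking denominator would be visible. The exclusion of incomplete patients is default software behaviour and not SAP wording. With few failures the model is fragile anyway: 3 failures over five candidates is 0.6 per covariate even if all 60 patients are complete.

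Most of this stands, and it limits the weight of the point. It does not remove it. The SAP names the procedure and overrides none of its defaults. Room to drop a sparse covariate is not a rule to do so. A single n shows that patients were lost, but not that they were lost to a covariate no longer in the model, nor how many failures remain.

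A reader might infer more: that elimination starts from all 18 covariates, that FibroTest is always among them, or that the final model will rest on a small subset. The documents do not support this. Only covariates that pass the screen enter, after collinearity handling. FibroTest enters only if it passes, which is unlikely when it is sparse and failures are few. No missingness rate is given, and without FibroTest the illustration keeps 46-54 of 60. Nor do the documents show that prothrombin time or alpha-fetoprotein will be especially sparse: Protocol section 9.8 lists prothrombin time (or INR) and alpha-fetoprotein among the Visit 1 laboratory items, beside ALT and albumin.

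**Conclusion.** The point holds as a minor gap in the exploratory modelling. As written, a patient missing any starting candidate is excluded throughout, so the final odds ratios can rest on a smaller, selected subset than the retained covariates require.

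The loss could be nil, or modest, at 6-14 of 60 patients when five routine candidates are each 95-98% complete. It could be large, at about 32-36 of 60, if a FibroTest available in half the patients passes the screen. These figures rest on assumed completeness, independent missingness, five candidates and N=60. Analyses in smaller populations or subgroups would start from fewer patients.

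The primary SVR12 percentage and its Clopper-Pearson interval do not depend on this modelling.

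**What to change.** In SAP section 9, add that if MLR is run:

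1. The covariates retained by backward elimination are refitted on all patients in the analysis set who have data for them.
2. That refit is presented as the final model.
3. The MLR tables (2.1.X.2, 2.2.X.2 and 2.3.X.2) show N and the number of failures for both the selection fit and the refit.

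The cost is a sentence or two in the SAP, extra rows in the shell, and one more model run per endpoint in each population where MLR is done. A retained covariate may no longer meet p<0.05 in the refit. It should then be reported as it is, without a further round of elimination.

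A completeness limit for MLR candidates, for example excluding those missing in more than 20% of patients, is optional. It would cover the case where a sparse covariate is itself retained, but the cut-off is only a convention. Neither step overcomes the small number of failures, so the results remain exploratory.
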